7.2.8 Safety Variables

Adverse Events (AE)

AE data are collected on the 'Adverse Events' eCRF page. Corrective medications or procedures due to an AE are documented on the eCRF pages 'Prior and Concomitant Medications' and 'Concomitant Procedures' respectively.

The AE Description (Investigator term) will be analyzed on Preferred Term (PT) and System Organ Class (SOC) level using MedDRA.

Based on the information provided on the 'Adverse Events' eCRF page, the following definitions will be utilized:

- An ocular event will be identified, if the question 'Is this an ocular event?' is answered 'Yes'.
- An AE with missing severity will be counted as severe.
- A Serious Adverse Event (SAE) is any adverse event where the question 'Is the event serious?' has been answered as 'Yes'. If this question is not answered the event will be considered as 'Serious' for analysis purposes.
- *The following adverse events are considered to be of special interest (AESI) and by default shall be reported as SAEs (medically important criteria):*
 - *AEs that caused a decrease in visual acuity of >30 ETDRS letters or > +0.6 LogMAR (compared with the last assessment of visual acuity at the last visit) lasting >1 hour*
 - *AEs that caused a decrease in visual acuity to the level of Light Perception or worse lasting >1 hour*
 - *AEs that required surgical intervention (e.g., conventional surgery, vitreous tap or biopsy with intravitreal injection of anti-infectives, or laser or retinal cryopexy with gas) to prevent permanent loss of sight*
 - *AEs associated with severe intraocular inflammation (i.e., 4+ anterior chamber cell/flare or 4+ vitritis)*
 - *AEs that, in the opinion of the Investigator, may require medical intervention to prevent permanent loss of sight.*

For analysis purposes, AESI will be identified by ticked box 'Medically significant or important medical condition' in the eCRF section 'SAE criteria'. This means in particular, that all AESIs will be considered as SAEs.

- An AE leading to premature withdrawal of the study treatment is defined as an AE where in the eCRF section 'Action taken with study treatment' the boxes 'Withdrawn' and 'Definitely' are ticked.
- An AE leading to study treatment interruption is defined as an AE where in the eCRF section 'Action taken with study treatment' the boxes 'Withdrawn' and 'Temporarily' are ticked.
- An AE leading to study discontinuation is defined as an AE where in the eCRF section 'Action regarding Patient' the box 'Patient Withdrawn' is ticked (this should match with the primary reason for early withdrawal of 'Adverse Event' on the End of Study eCRF page).
- An AE is classified as 'Related' to Study Treatment if the relationship to study medication recorded as 'Possible' or 'Probable' or 'Highly Probably'. An AE will be classified as unrelated to study medication if the relationship to study medication was recorded as 'None' or 'Unlikely'. AEs with missing relationship to study treatment will be counted as 'Related' to Study Treatment.
- A Fatal AE is defined as an AE where the outcome is recorded as 'Fatal'.

These definitions will apply accordingly also for the subsequent sub-classes of AEs.

Non Treatment-emergent adverse events (Non-TEAEs)

A Non-TEAE is defined as any AE, which started before the first administration of study treatment. They are identified by the ticked box 'Before Treatment Period' in the eCRF Section 'Did the event occurred:'.

Treatment-emergent adverse events (TEAEs)

A treatment-emergent adverse event is defined as an AE that started on or after the date of the First Study Treatment Administration. A TEAE will be identified, if The eCRF question 'Did the event occurred:' was answered either with 'During Treatment period' or 'During Follow-Up Period'.

The incidence and frequency of TEAEs will serve as safety endpoint of the study.

TEAEs in the Treatment Period

This will be defined as a TEAE (as defined above) with a start date on or after the date of first study treatment administration and before the Week 8 Visit. It will be identified, if eCRF question 'Did the event occurred:' was answered with 'During Treatment period'.

TEAEs in the Follow-up Period

This is defined as a TEAE (as defined above) with a start date on or after the Week 8 Visit. It will be identified, if eCRF question 'Did the event occurred:' was answered with 'During Follow-Up period'.

For listing purposes, treatment day of onset of AE will be presented according to the definition given in section 7.1.

Missing Codes or Incomplete AE start dates:

In the event that coding information will not be available for a specific AE, the event will be presented as 'Uncodable Event'). However, for final TLFs it is anticipated that all events are coded.

If the eCRF question 'Did the event occur:' was not answered, AEs will be classified to subclass Non-TEAEs, TEAE in the Treatment Period or TEAE in the Follow-up Period based on the AE onset date utilizing the definitions given above. If this is not possible, the event will be classified as TEAE in the Treatment Period.

Missing and/or incomplete AE onset dates will be imputed for calculating relative start and stop days only. Dates will be listed as missing/incomplete [with "-" replacing missing information] but the onset Day listed between square brackets to denote it was calculated based on missing data (i.e. [1]).

Missing and/or incomplete dates will be imputed in a manner that assumes the worst case scenario:

- For a missing start day (but month and year is available), onset is assumed on the first day of the respective month.

- For a missing start month (but year is available), onset is assumed on 1st January of the respective year.
- For a completely missing start date, no imputation will be performed.

If for Non-TEAEs this procedure results in an onset date before date of informed consent, informed consent date will be used.

If for TEAEs 'During treatment period' this procedure results in an onset date before date of first study treatment, date of first study treatment will be used.

If for TEAEs 'During Follow-Up period' this procedure results in an onset date before date of Week 8 visit, date of Week 8 visit will be used.

Best Corrected Visual Acuity (BCDVA)

Best-corrected visual acuity is measured at Day 0 Baseline, Week 8 and Week 12 visit using standard charts, lighting, and procedures. All eyes must be tested at 4 meters first. When a patient cannot read at least 20 letters on the chart at 4 meters, the patient is tested at 1 meter.

In addition, the Snellen Equivalent is collected, which is based on smallest line read correctly (i.e. no or max. 1 error). The Scale is categorical and does not easily lend itself to statistical analysis or easy comparison but the logarithm of the minimal angle of resolution (logMAR) scale allows visual acuity to be assessed as a continuous measurement.

Visual acuity is recorded on the eCRF page 'Best Corrected Distance Visual Acuity'.

For the analysis, the BCDVA score and the logMAR as well as respective changes from baseline will be evaluated at Week 8 and Week 12. No imputation will be envisaged for these endpoints.

The BCDVA score will be derived as the total numbers of letters, which were read correctly at 4 meter plus the total number of letters read at 1 meter as collected on the eCRF page.

When 20 or more letters are read at 4 meters the visual acuity score (i.e. BCDVA score) for that eye is recorded as the number of letters correct at 4 meters plus 30. The patient gets credit for the 30 letters at 1 meter even though they did not have to read them. If no letters are read correctly at either 4.0 meters or 1 meter, then the visual acuity score is recorded as "0."

The logMAR will be derived as $-\log$ (Snellen Equivalent result). For this derivation the Snellen equivalent result is presented as fraction as documented in the eCRF field 'Snellen Equivalent Result'. LogMAR values derived from Snellen equivalent results range from -0.3 (20/10) to 1.6 (20/800) and will be rounded by 2 decimals. An increase in logMAR reflects a worsening of visual acuity.

If for a patient only ability for counting fingers is reported, logMAR will be set to 2; if for a patient only recognition of hand motion is reported, logMAR will be set to 3 [1].

Slit lamp examination

Slit lamp examination is performed separately for each eye at Baseline, Week 4, Week 8 and Week 12 visit and is recorded on the eCRF page 'Slit Lamp Examination (Biomicroscopy)'.

Grading of the eyelids, lashes, conjunctiva, cornea, lens, iris and anterior chamber will be done according to the following scales:

Eyelid - Meibomian glands

- 0 = None (none are plugged).
- 1 = Mild (1 to 2 glands are plugged).
- 2 = Moderate (3 to 4 glands are plugged).
- 3 = Severe (All glands are plugged).

Eyelid - Erythema

- 0 = None (normal).
- 1 = Mild (redness localized to a small region of the lid(s) margin OR skin).
- 2 = Moderate (redness of most or all lid margin OR skin).
- 3 = Severe (redness of most or all lid margin AND skin).
- 4 = Very severe (marked diffuse redness of both lid margin AND skin).

Eyelid - Edema

- 0 = None (normal).
- 1 = Mild (localized to a small region of the lid).
- 2 = Moderate (diffuse, most or all lid but not prominent/protruding).
- 3 = Severe (diffuse, most or all lid AND prominent/protruding).
- 4 = Very severe (diffuse AND prominent/protruding AND reversion of the lid).

Lashes

- 0 = Normal
- 1 = Abnormal

Conjunctiva – Erythema

- 0 = None (normal).
- 1 = Mild (a flush reddish color predominantly confined to the palpebral or bulbar conjunctiva).
- 2 = Moderate (more prominent red color of the palpebral or bulbar conjunctiva).
- 3 = Severe (definite redness of palpebral or bulbar conjunctiva).

Lens

- 0 = No opacification (normal lens).
- 1 = Mild lens opacification.
- 2 = Moderate lens opacification.
- 3 = Severe lens opacification.

Iris

- 0 = Normal
- 1 = Abnormal.

Anterior Chamber Inflammation

- 0 = None (no Tyndall effect).
- 1 = Mild (Tyndall effect barely discernible).
- 2 = Moderate (Tyndall beam in the anterior chamber is moderately intense).
- 3 = Severe (Tyndall beam in the anterior chamber is severely intense).

All grading assessments of different eye structures will be evaluated as collected on the eCRF at Baseline Visit, Week 4, Week 8 and Week 12. No imputation will be envisaged for these parameters.

No aggregated presentation is planned for other assessments done during Slit lamp evaluation.

External ocular examination

External Ocular Examination assesses the motility of the extraocular muscles and the appearance and function of the eyelids before the instillation of any dilating or anesthetic eye drops.

Motility of extraocular muscle and appearance/function of eye lids is assessed separately for each eye at Baseline, Week 4, Week 8 and Week 12 visit and is recorded on the eCRF pages 'External Ocular Examination' and 'Appearance and Function of Eyelids'.

For the analysis, the Motility of the Extraocular Muscle will be evaluated by the field of movements Right and up ('Normal', 'Abnormal'), Right ('Normal', 'Abnormal'), Right and Down ('Normal', 'Abnormal'), Left and Up ('Normal', 'Abnormal'), Left ('Normal', 'Abnormal'), Left and Down ('Normal', 'Abnormal') as documented at the eCRF at Baseline Visit, Week 4, Week 8 and Week 12. No imputation will be envisaged for these parameters.

Appearance and Function of Eyelids will be summarized by the following parameters:

- Incidence of proven eyelid deformity/abnormality, which will be considered as present, if the question 'Evidence of eyelid deformity or abnormality' on the eCRF page 'Appearance and Function of Eyelids' is answered 'Yes'.
- Incidence of abnormal motor function of eyelids (i.e. upper lid elevation and forceful lid closure), which will be considered as present, if the question 'Motor function of eyelids' on the eCRF page 'Appearance and Function of Eyelids' is answered 'ABNORMAL'.
- Incidence of corneal exposure in case of closed eyelids, which will be considered as present, if the question 'Is there corneal exposure when the eyelids are closed?' on the eCRF page 'Appearance and Function of Eyelids' is answered 'Yes'.
- Incidence of proven punctual occlusion, which will be considered as present, if the question 'Is there evidence of punctual occlusion?' on the eCRF page 'Appearance and Function of Eyelids' is answered 'Yes'.
- Incidence of punctual plugs, which will be considered as present, if the box 'Punctual plugs' is ticked on the eCRF page 'Appearance and Function of Eyelids'.

- Incidence of thermal or surgical occlusion, which will be considered as present, if the box 'Thermal or surgical occlusion' is ticked on the eCRF page 'Appearance and Function of Eyelids'.
- Incidence of Other punctual occlusion, which will be considered as present, if the respective 'Other' box is ticked on the eCRF page 'Appearance and Function of Eyelids'.

8 Analysis Methods

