#### **11.1.3 Serious Adverse Event (SAE)**

A serious adverse event (SAE) is defined in line with Directive 2001/20/EC as any adverse experience that meets any of the following criteria:

- results in death
- is life-threatening

(NOTE: Life-threatening means that the patient was at immediate risk of death from the reaction as it occurred, i.e., it does not include a reaction which hypothetically might have caused death had it occurred in a more severe)

- requires inpatient hospitalization or prolongation of existing hospitalization

(NOTE: In general, hospitalization means that the individual remained at the hospital or emergency ward for observation and/or treatment (usually involving an overnight stay) that would not have been appropriate in the physician's office or an out-patient setting. Complications that occur during hospitalization are AEs. If a complication prolongs hospitalization or fulfils any other serious criteria, the event is serious. When in doubt as to whether “hospitalization” occurred, the event should be considered serious

- results in persistent or significant disability/incapacity

(NOTE: The term disability means a substantial disruption of a person's ability to conduct normal life functions. This definition is not intended to include experiences of relatively minor medical significance such as uncomplicated headache, nausea, vomiting, diarrhoea, influenza, or accidental trauma (e.g., sprained ankle) which may interfere or prevent everyday life functions but do not constitute a *substantial disruption*)

- results in a congenital anomaly/birth defect
- is an important medical event

(NOTE: An important medical event is an event that may not result in death, be life-threatening, or require hospitalization but may be considered a SAE when, based upon appropriate medical judgment, it may jeopardize the patient's well-being and may require medical or surgical intervention to prevent one of the outcomes listed in the definitions for SAEs. Examples of such medical events include allergic bronchospasm requiring intensive treatment in an emergency room or at home, blood dyscrasias or convulsions that do not result in patient hospitalization or the development of drug dependency or drug abuse)

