#### **11.2 Adverse Events of Special Interest (Sight-threatening Events)**

The following adverse events are considered to be of special interest and by default shall be reported as SAEs (medically important criteria):

- Adverse Events that caused a decrease in visual acuity of >30 ETDRS letters or > +0.6 LogMAR (compared with the last assessment of visual acuity at the last visit) lasting >1 hour

- Adverse Events that caused a decrease in visual acuity to the level of Light Perception or worse lasting >1 hour
- Adverse Events that required surgical intervention (e.g., conventional surgery, vitreous tap or biopsy with intravitreal injection of anti-infectives, or laser or retinal cryopexy with gas) to prevent permanent loss of sight
- Adverse Events associated with severe intraocular inflammation (i.e., 4+ anterior chamber cell/flare or 4+ vitritis)
- Adverse Events that, in the opinion of the Investigator, may require medical intervention to prevent permanent loss of sight.

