9.6 Safety Results

9.6.1 Adverse Events

9.6.1.1 Brief Summary of Adverse Events

Reporting of AEs is focused to treatment emergent AEs.

An overview of AEs, TEAEs, TEAEs during Treatment Period, TEAEs during Follow-up Period, TEAEs leading to premature withdrawal of the study treatment. TEAEs leading to study discontinuation, serious TEAEs, Fatal TEAEs, treatment related TEAEs, treatment related serious TEAEs, TEAEs of special interest and Mild, Moderate and Severe TEAEs will be given by study treatment and overall for patients in the SAF. For each events, the number and percentages of patients with at least one event as well as the total number of events will be provided.

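### SAP 7.2.8 identifies events of special interest by a generic SAE box rather than by the five sight-threatening criteria, so the AESI line of the AE overview can count events that are not AESIs

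*SAP*

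**What the plan says.** Protocol 11.2 equates AESIs with sight-threatening events and introduces five criteria with the words "The following adverse events are considered to be of special interest and by default shall be reported as SAEs (medically important criteria"). In short, the criteria are:

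1. loss of more than 30 ETDRS letters, or more than 0.6 logMAR, lasting over an hour;
2. loss to light perception or worse, lasting over an hour;
3. surgery needed to prevent permanent loss of sight;
4. severe intraocular inflammation;
5. the investigator's opinion that medical intervention may be needed to prevent permanent loss of sight.

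SAP 7.2.8 repeats the five criteria and then gives the working rule: "For analysis purposes, AESI will be identified by ticked box". The box is the one for a medically significant or important condition in the SAE-criteria section of the eCRF. No other condition is attached. The SAP draws one consequence: "This means in particular, that all AESIs will be considered as SAEs".

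Of its AE definitions, the same section says "These definitions will apply accordingly also for the subsequent sub-classes of AEs". SAP 9.6.1.1 then puts "TEAEs of special interest and Mild, Moderate and Severe TEAEs" among the lines of the AE overview, by treatment and overall, for the Safety Set. For each line, "the number and percentages of patients with at least one event as well as the total number of events will be provided".

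**The concern.** The protocol's statement runs one way: an event that meets a criterion is reported as a medically important SAE. The SAP rule runs the other way and treats every event with the medically important box ticked as an AESI. The five criteria are printed but play no part in the derivation.

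At stake is the meaning of one safety line. A reader who sees a count of TEAEs of special interest will take it, from protocol 11.2, as a count of sight-threatening events. Under the SAP rule it can also contain medically important events that have nothing to do with sight.

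**Working it through.** The plan states no figure that depends on this rule, so there is nothing to reproduce. The check is a comparison of texts, followed by simple arithmetic on the planned group sizes.

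**Step 1: direction of the definition.**
- Protocol 11.2: meets a sight criterion → medically important SAE.
- SAP 7.2.8: medically important box ticked → AESI.

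The second is the converse of the first. It would be harmless only if the box were used for nothing but sight-threatening events.

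**Step 2: is the box specific to sight?** No. Protocol 11.1.3 makes the important medical event a general seriousness criterion: "Examples of such medical events include allergic bronchospasm requiring intensive treatment in an emergency room or at home, blood dyscrasias or convulsions". None of these meets any of the five criteria.

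**Step 3: does the error reach an output?** Yes. The AE definitions carry over to the sub-classes, which include TEAEs, and the AE overview has a line for TEAEs of special interest. A treatment-emergent convulsion with the box ticked is counted there.

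**Step 4: does anything else restore the criteria?**
- The ocular question on the AE page is collected but is not part of the AESI rule.
- SAP 3.7, which lists departures from the protocol's analysis, does not mention the rule.
- The blinded data review meeting (SAP 6.1 and 7.1) is described for analysis sets, main eyes, protocol deviations and visit conformance, not for AESIs.

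**Step 5: the reverse error.** A sight-threatening event whose box is not ticked is missed. This needs the site to depart from the default in protocol 11.2. One route is a blank seriousness question. SAP 7.2.8 says "If this question is not answered the event will be considered as" serious, but no rule fills in the box, so such an event is an SAE in the analysis without being flagged as an AESI.

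**Step 6: what the other outputs show.** A wrongly counted TEAE also appears by preferred term in Table 14.3.2-3.1 (all TEAEs), 14.3.2-5.1 (serious TEAEs), 14.3.2-12.1 (by severity), and 14.3.2-10.1 or 14.3.2-11.1 (by period). It is listed in 16.2.7-1.1 and 16.2.7-1.5. None of the 11 AE tables in SAP 9.6.1.2, and none of the 7 listings 16.2.7-1.1 to 16.2.7-1.7, is dedicated to AESIs.

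**Step 7: size per patient.** Inputs: 120 rhNGF and 60 vehicle patients (protocol synopsis, Number of Subjects), assuming the Safety Set equals the planned enrolment. One patient with such a TEAE and no true AESI adds:
- rhNGF column: 1/120 = 0.83 percentage points;
- vehicle column: 1/60 = 1.67 percentage points;
- overall column: 1/180 = 0.56 percentage points.

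Each such event also adds one to the event count on that line.

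**The case against.** The strongest defence is that the SAP states its proxy openly and that the proxy errs mainly towards over-counting. This is in keeping with other defaults in SAP 7.2.8: missing severity counts as severe, missing seriousness as serious, missing relationship as related. How often the box is ticked for non-sight events depends on how the site was told to use it. Protocol 12.1 says eCRF completion will be explained, but that guidance is not in the documents. AESI is not an endpoint and no test uses it.

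Most of this stands, and it limits the point to a minor one. It does not remove it. The other defaults deal with missing answers, whereas this rule reclassifies events that are fully recorded, under a label the protocol reserves for something narrower.

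A reader might infer that the make-up of the AESI line cannot be traced. The documents do not support that. SAP 9.6.1.3 says the listings present all AE data by patient, which as written would include the box and the ocular answer. The mock shells that fix the columns are a separate document. What remains is narrower: no planned output is shown to give the criterion each event met.

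A reader might also infer that sight-threatening events will be lost. That follows only if the site does not apply the protocol 11.2 default.

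**Conclusion.** The rule is wrong as written, and the consequence is small. A treatment-emergent event that has the box ticked and meets none of the five criteria is counted as a TEAE of special interest. Nothing in the protocol or SAP corrects this.

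The effect is limited to one descriptive line of the AE overview. The misclassification leaves the SAE and TEAE totals, the TEAE safety endpoint and the efficacy analyses unchanged, so it would be wrong to read it as a flaw in the safety assessment as a whole.

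The per-patient size is 0.8 points (rhNGF), 1.7 points (vehicle) or 0.6 points (overall), on the assumption that the Safety Set equals the planned 120 and 60. The documents give no expected number of medically important events. The total effect may therefore be zero, and no probability or share of false AESIs can be stated.

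**What to change.** In SAP 7.2.8, define an AESI as an adverse event that meets at least one of the five protocol 11.2 criteria, and use the box only to find candidates. Then:

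- At the planned blinded data review meeting, before unmasking, check two groups against the five criteria: all SAEs, whether or not the box is ticked and whether or not they are marked ocular; and all non-serious AEs that are ocular or have the ocular question blank.
- Where a non-serious event appears to meet a criterion, query the site so that its seriousness is reconciled with protocol 11.2.
- Add the criterion met to the AE listing.

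The review will rest on AE descriptions and site queries rather than on the scheduled examinations. Visual acuity is measured only at baseline, Week 8 and Week 12, so it cannot show how long a loss lasted. The SAP's anterior chamber scale stops at grade 3, so it cannot confirm the 4+ criterion.

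If the sponsor prefers to keep the box rule, the alternative is to relabel the line as medically important serious TEAEs and not call it AESI.

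Cost: a short SAP edit, one added listing column, a small masked review and possibly a few site queries before database lock. The relabelling alternative costs only the change of wording.

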## **10.6 Safety and tolerability evaluation**

### **AEs**

Adverse events (AEs) will be coded by System Organ Class (SOC) and Preferred Term (PT), using the Medical Dictionary for Regulatory Activities (MedDRA).

TEAEs are all events occurring or worsening after the first dose of the IMP.

Individual AEs/TEAEs will be listed in patient data listings. TEAEs will be summarized by treatment. The number and percentage of patients with any AE and the number of TEAEs will be tabulated by SOC and PT, seriousness, relationship to treatment and severity.

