**Table 11.4.1 Relationship of the Adverse Event to the Investigational Product**

None (Intercurrent Event)	An event that is not and cannot be related to the investigational product, e.g. patient is a passenger in a road traffic accident
Unlikely (remote)	Relationship is not likely e.g. a clinical event including laboratory test abnormality with temporal relationship to drug administration which makes a causal relationship improbable and in which other drugs, chemicals or underlying disease provide plausible explanations
Possible	Relationship may exist, but could have been produced by the patient's condition or treatment or other cause
Probable	Relationship is likely, the AE abates upon discontinuation of investigational product and cannot be due to the patient's condition
Highly Probable	Strong relationship, the event abates upon discontinuation of investigational product and, if applicable, re-appears upon repeat exposure

Severity of AEs

The Investigator will grade the severity of any AE using the definitions in the Table below. For each episode, the highest severity grade attained should be reported.

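### SAP 7.2.8 defines treatment-emergent adverse events by when they start and silently drops the worsening limb in protocol 10.6

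*SAP*

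**What the plan says.** Protocol 10.6 gives the definition on which the safety evaluation rests: "TEAEs are all events occurring or worsening after the first dose of the IMP". It has two limbs, new events and worsening events.

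SAP 7.2.8 keeps only the first: a TEAE "is defined as an AE that started on or after the date of the First Study Treatment Administration". The complementary class is set in the same way: "A Non-TEAE is defined as any AE, which started before the first administration of study treatment". In practice an eCRF question on the period of occurrence decides. Of Non-TEAEs the SAP says "They are identified by the ticked box 'Before Treatment Period' in the eCRF Section", and TEAEs are those marked as occurring during treatment or follow-up. If the question is unanswered, the event is classified "based on the AE onset date utilizing the definitions given above". If that also fails, it becomes a TEAE in the treatment period.

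On the role of this class the SAP is explicit: "The incidence and frequency of TEAEs will serve as safety endpoint of the study". Protocol 2.3 names no other safety end-point, and protocol 9.1.1 lists TEAEs among the primary variables.

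On recording, protocol 11.4 has adverse events documented from consent onwards and adds, on severity: "For each episode, the highest severity grade attained should be reported".

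**The concern.** A SAP may narrow a protocol definition, but it should say so. SAP 3.7 lists four departures and clarifications: endpoint presentation, screen failures, compliance and exploratory inference. The TEAE definition is not among them, so someone reading the study report would assume that the protocol definition had been applied.

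The events at issue are those that a treatment-emergent definition with a worsening limb is meant to catch: something already present at the first dose that gets worse on drug. The situation is plausible here. Day 0 includes fluorescein instillation, contact aesthesiometry and, in LASIK patients, confocal microscopy, all before home dosing starts (protocol 6.1 and 7.1). SAP 9.6.1 concentrates on TEAEs: the tables by severity, relationship, seriousness, withdrawal of treatment and study discontinuation are all limited to them. A pre-dose event that worsened and led a patient to stop treatment would be absent from each of those tables.

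**Working it through.** No sample size, power or event count enters this point, and the plan states no figure to reproduce. The check is to take the possible adverse event records and classify each under both documents.

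| Adverse event record | Protocol 10.6 | SAP, period box ticked | SAP, box blank (onset date) |
|---|---|---|---|
| Starts after the first dose | TEAE | TEAE | TEAE |
| Starts on a date before the first dose, does not worsen | Not a TEAE | Non-TEAE | Non-TEAE |
| Starts on a date before the first dose, worsens on treatment, one record | TEAE | Non-TEAE | Non-TEAE |
| Starts on a date before the first dose, worsening entered as a new event | TEAE | New line is a TEAE | New line is a TEAE |
| Starts on the day of first dose but before it, does not worsen | Not a TEAE | Non-TEAE if marked as before treatment | Meets both SAP definitions |
| Starts on the day of first dose but before it, worsens, one record | TEAE | Non-TEAE if marked as before treatment | Meets both SAP definitions |

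Three things follow.

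1. **Row three is a direct contradiction.** Neither the tick box nor the date fallback looks at the later course of the event. No other SAP text reclassifies it; the SAP uses the idea of worsening only to explain the direction of logMAR.

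2. **Rows three and four differ only in recording practice.** Protocol 11.4 asks for the highest grade per episode and, where possible, one comprehensive event for related signs and symptoms. Its required fields include onset and resolution dates but no date of worsening. This points towards a single record without requiring one. Protocol 11.3 asks that clinically relevant untoward changes in protocol parameters or questionnaire responses be reported as events, but does not say that worsening of an existing event needs a new line.

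3. **Rows five and six show a second defect.** The SAP's TEAE wording works from the date of first administration, and its Non-TEAE wording from the administration itself. An event that begins at the Day 0 visit, with the first dose taken later that day, satisfies both. The tick box settles it in practice; the date fallback does not.

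A row-three event, or a row-six event marked as before treatment, stays in the all-AE count of the overview (SAP 9.6.1.1), the Non-TEAE table (9.6.1.2), the listing of all adverse events and, if serious, the serious AE listing (9.6.1.3). It is missing from TEAE incidence and from every TEAE table and TEAE-only listing.

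**The case against.** The strongest reply is that the wording differs but little is lost.

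- **The window is short.** Consent, randomization and dispensing all take place at the Day 0 visit, and patients start treatment after it. Few adverse events can start in between. This stands.
- **Worsening of older conditions has its own route.** Conditions present before consent are recorded separately, and their worsening can enter as a new event with an on-treatment onset. This also stands. A reader might infer that every condition present before the first dose escapes the endpoint if it worsens; the documents do not support that.
- **The single record is an inference.** The highest-grade instruction applies per episode and does not say that a pre-dose event and its later worsening are one episode. The eCRF completion instructions are not in the documents. This stands as a limit on how often the problem arises.
- **Day 0 irritation is not automatically lost.** A reader might infer that an event provoked by Day 0 procedures is always a Non-TEAE. That depends on the tick box, because a same-day event also meets the SAP's date-based TEAE wording.
- **The rule does not only undercount.** The missing limb can only remove events, but the rule as a whole also has inclusive parts: the same-day date wording, and the default of unclassifiable events to TEAE.
- **The effect falls on both masked arms.** The definition is the same for each, and no test on TEAEs is planned. This limits the scope for a biased comparison but does not make the counts match the protocol.

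None of these points removes the contradiction or its absence from SAP 3.7.

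**Conclusion.** The point holds as an undeclared departure from the protocol on the trial's only safety endpoint. It should be corrected, but it does not threaten the trial.

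The wording mismatch is certain. A loss of events follows only under conditions: the event is recorded as starting after consent and before the first dose, it worsens on treatment, and it is kept as one record classed by its start.

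The number of such events cannot be derived from the documents. A reader might want to put a figure on it. If, purely by assumption, 2% to 5% of patients had such a pre-dose event and half of these worsened, 120 × 0.02 × 0.5 = 1.2 to 120 × 0.05 × 0.5 = 3 patients on rhNGF would be affected, and by the same sum 0.6 to 1.5 of 60 on vehicle. The documents support neither rate, and the window may be a matter of hours, so this is not an estimate of the loss. What can be said is that the number is probably small.

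The overlap of the two SAP definitions on the day of first dose is a separate, minor defect in the same section.

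**What to change.** In SAP 7.2.8, define a TEAE as an adverse event that starts after the first dose, or starts before it and worsens after it, in line with protocol 10.6. Then make the rule workable:

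- Instruct sites to enter post-dose worsening of an existing event as a new line with its own onset date, so that the period box and the date fallback both pick it up. The highest-grade instruction then applies within each line, and the pre-dose line keeps its pre-dose grade.
- Say what counts as worsening, since the protocol does not. A rise on its three-grade severity scale is the obvious candidate.
- At the blinded data review meeting, before unmasking, check adverse event records already entered as pre-dose for later worsening.
- State how a pre-dose event on the day of first dose is classed, so that the TEAE and Non-TEAE definitions no longer overlap.

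If the sponsor prefers the start-only definition, it should be listed and justified in SAP 3.7.

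The cost is a short SAP edit, an eCRF completion note and minor extra data review. TEAE counts may rise slightly, and an event that worsens will appear once in the Non-TEAE table and once in the TEAE tables.
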